## 1.0 Protocol Summary

Study Purpose	

• It is to evaluate the tolerability and efficacy of the Oxygenating Bite Block (OBB).

Research Procedures	

• Utilize the Oxygenating Bite Block during endoscopy procedure,

• Questionnaire for the patient,

• Questionnaire for anesthesiologist, and

• Questionnaire for gastroenterologist.

Subject Population	Ten obese patients scheduled to undergo: 

• upper endoscopy,

• esophageal-gastro duodenoscopy (EGD),

• endoscopic ultrasound (EUS), or

• endoscopic retrograde cholangiopancreatography (ERCP).

Duration of Subject's Participation	

• One visit/One day

## 2.0 Background, Rationale

Hypoxemia due to respiratory depression or airway obstruction is a known risk associated with endoscopic procedures, with studies showing that hypoxemia occurs in 11–50% of cases [1].

The current standard for oxygenating and monitoring a sedated patient for endoscopy has not evolved since the advent of capnography over 30 years ago. The procedure for sedation for upper endoscopy, ERCP and Transesophageal Echocardiography from an anesthetist's standpoint is as follows: A bite block is placed to protect the teeth and maintain oral latency for scope placement. A choice is then made to use either a face mask with a hole cut to pass the endoscope through, or to use a nasal cannula to oxygenate and monitor respirations. The face mask can easily be pushed into the patients' eyes inadvertently by the endoscopist creating a safety hazard, or the nasal cannula can be used which provides a lower fractional oxygen concentration.

This Oxygenating Bite Block (OBB) overcomes both problems and additionally it improves on both monitoring and oxygenating. The oxygen is delivered at the distal portion of the scope guide which reduces the anatomic dead space that the oxygen is required to overcome before reaching the lungs. Sedated patients loose muscle tone and have a reduced ability to ventilate their lungs with fresh air. The endoscopists often use CO2 to insufflate while they are examining the patient and the CO2 is 20x as diffusible as oxygen - requiring the O2 being delivered to overcome the diffusion gradient of CO2 coming from the esophagus. This reduction in dead space and improved oxygenation should make sedation safer. An additional improved safety aspect of this device is the integrated ETCO2 monitor which can be attached to a

capnography machine and monitor to ensure the sedated patient is breathing well. The ETCO2 is sampled from inside the mouth which is a more accurate sampling location. Additionally, sedation for endoscopies with propofol is increasingly being done by non-anesthetists. Propofol is a significant respiratory depressant, and the incidence of complications and hypoxemia is higher when the endoscopist uses propofol without an anesthetist present [2]. The oxygenating bite block is designed to improve oxygenation and monitoring in these situations.

### **Differences between the OBB and the Oral Airway**

The conventionally used Anesthesia and sedation support device is known as an 'Oral Airway'. Our study device is called the OBB. Both the OBB and the Oral Airway are small disposable devices that go in the mouth with the same basic form and size. The OBB is an oral airway that delivers oxygen, ***thus eliminating the need for a separate oxygen delivery product*** like a nasal cannula or face mask. The OBB delivers oxygen closer to the glottic opening in the retro pharynx, thus eliminating 'dead space'. Dead space is a space where Oxygen/CO2 exchange does not occur.

Additionally, the OBB has an OS (or 'mouth' of the device) where an endoscope can be placed and the ETCO2 sampling occurs via tubing attached to the device. This allows ETCO2 sampling to improve safety for sedated patients. By oxygenating and monitoring ETCO2, the OBB is just an advanced and safer oral airway. This novel device is not sufficiently different in dimensions or use than currently existing technology.

The OBB has a slightly thinner flange than the Oral Airway and a larger opening at the mouth which is identical to the existing bite blocks currently in use. This larger opening will allow the OBB to be used during endoscopy sedation. The commonly used 'Oral Airway' cannot be used during endoscopy sedation due to the thickness of the flange and the limited space between the teeth, which prevents passage of an endoscope.

The Oxygenating Bite Block (OBB) we are using for this study does not hold FDA 510k clearance, therefore this device would be categorized as an investigational, non-significant risk device due to the following reasons:

- Is NOT intended as an implant and does NOT present a potential for serious risk to the health, safety, or welfare of a subject.
- Is NOT purported or represented to be for use supporting or sustaining human life and does NOT present a potential for serious risk to the health, safety, or welfare of a subject;
- Is NOT for a use of substantial importance in diagnosing, curing, mitigating, or treating disease, or otherwise preventing impairment of human health and does NOT present a potential for serious risk to the health, safety, or welfare of a subject; or
- Does NOT otherwise present a potential for serious risk to the health, safety, or welfare of a subject.

- Does NOT meet device exemption criteria.

### 3.0 Study Purpose and Objectives

The primary objectives of this study are:

- 1) To evaluate the tolerability and efficacy of the Oxygenating Bite Block during sedation for endoscopic procedures.
- 2) To evaluate the Oxygenating Bite Block from the endoscopist and anesthesiologist perspective. These professionals will be part of the study team.

The secondary objectives of this study are:

- 1) To collect preliminary answers regarding the physician and patient tolerability and feasibility of the OBB through questionnaires.

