### **5.2 Study Design and Duration**

This a prospective, observational pilot study that aims to evaluate an Oxygenating Bite Block prototype in obese patients undergoing endoscopy. The endoscopy procedure nor the anesthesia management will change from current practices. The investigators will

hand out a short questionnaire to the patient, anesthesiologist, and endoscopist following the procedure regarding tolerability and/or feasibility of the device.

The duration of the study is about one day.

The study will be conducted on-site at Cedars-Sinai.

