### **5.3 Description of Study Procedures**

The study involves participation at a single timepoint only. The study procedures to be done are listed below.

The only data to be collected are three questionnaires. Following the procedure, the patient, anesthesiologist, and gastroenterologist will be given a short questionnaire administered in-person regarding the tolerability and feasibility of the OBB.

The following will be collected and analyzed from the patient questionnaire:

- 1) Satisfaction of sedation level during the procedure
- 2) Tolerability of the OBB
- 3) Presence of a sore throat

The following will be collected and analyzed from the anesthesiologist questionnaire:

- 1) Ease of use of the OBB
- 2) Adequacy of teeth protection
- 3) Efficacy of oxygenation of the OBB
- 4) Efficacy of oxygenation in comparison with currently available alternatives for MAC
- 5) Efficacy of ETCO2 monitoring
- 6) Potential future use of the OBB
- 7) Desaturation of patient
- 8) Professional opinion of the OBB

The following will be collected and analyzed from the gastroenterologist questionnaire:

- 1) Patient tolerability of the OBB
- 2) Potential future use of the OBB
- 3) Interference of the OBB with endoscopy performance
- 4) Professional opinion of the OBB

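### Efficacy is a primary objective, but one group of 10 patients assessed by questionnaire can only describe clinician-rated performance, and the one comparative item names no comparator

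*Combined protocol and SAP*

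**What the plan says.** - **Objective.** The first primary objective in 3.0 is "To evaluate the tolerability and efficacy of the Oxygenating Bite Block during sedation for endoscopic procedures". The study purpose in 1.0 also names efficacy. The second primary objective is an evaluation from the clinicians' perspective, and 3.0 places those clinicians on the study team. The secondary objective is narrower: "To collect preliminary answers regarding the physician and patient tolerability and feasibility of the OBB through questionnaires".
- **Design.** Section 5.2 describes a "prospective, observational pilot study that aims to evaluate an Oxygenating Bite Block prototype in obese patients undergoing endoscopy" and adds: "The endoscopy procedure nor the anesthesia management will change from current practices". Section 8.1 sets 10 subjects. No control arm, crossover, period on another oxygen source or historical control is described.
- **Data.** Section 5.3 limits data collection to three questionnaires given after the procedure, and 6.1 says medical records are not accessed. The anesthesiologist items include efficacy of oxygenation (item 3), "Efficacy of oxygenation in comparison with currently available alternatives for MAC" (item 4), efficacy of ETCO2 monitoring (item 5) and desaturation (item 7). Desaturation has no stated threshold or duration.
- **Usual practice.** Section 2.0 gives the usual choice as "a face mask with a hole cut to pass the endoscope through, or to use a nasal cannula", and says the cannula delivers the lower oxygen concentration.
- **Analysis.** Section 8.3 plans frequencies and percentages, compared between questionnaires. No comparison between devices, test, benchmark or success criterion is given.

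**The concern.** The first primary objective asks a question that the design cannot answer in relative terms. Efficacy of an oxygen-delivery device is naturally read as a benefit over how these patients would otherwise have been oxygenated, and nothing in the study shows what would have happened to them on usual oxygen. A low desaturation count therefore could not be credited to the device.

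Item 4 is the only comparative datum, and it is a clinician's opinion. As listed, it does not say which alternative is meant. One anesthesiologist may have a cannula in mind and another a mask, and the protocol itself says the two differ. A single percentage over all answers would then have no clear meaning. The raters belong to the study team and no blinding is described, so the answers also need to be labelled as opinion. What is at stake is how the results may be worded when the pilot is reported or used to justify a later study.

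**Working it through.** **1. Objective set against design.** A conclusion of relative efficacy needs an outcome on the OBB and an outcome, or an agreed benchmark, without it. Sections 5.2, 5.3 and 8.1 supply only the first. Section 8.3 compares questionnaires, not devices. What the data can give is a set of descriptive proportions: clinician-rated oxygenation, ETCO2 monitoring, teeth protection, ease of use and reported desaturation.

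**2. Item 4 set against section 2.0.** Item 4 refers to alternatives in the plural. Section 2.0 names two, mask and cannula, with different oxygen concentrations. No alternative is a study condition, so the rater's reference is presumably past experience. If the form leaves the reference open, a pooled percentage averages answers to different questions.

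**3. The plan's own figure.** The sample size is 10 (8.1). Section 8.2 says no justification is required for a pilot of at most 20 subjects. No error rate, power, effect size or precision target is given, so there is nothing to reproduce. That is not an error in itself for a pilot.

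**4. Illustration: how far could a desaturation count go on its own?**

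Inputs: n = 10 (8.1) and the background statement "with studies showing that hypoxemia occurs in 11–50% of cases" (2.0). The protocol does not adopt this range as a benchmark. Assumptions: patients are independent with a common rate p, and the undefined desaturation item counts the same event as the background hypoxemia figure.

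- Expected events: 10 × 0.11 = 1.1, up to 10 × 0.50 = 5.
- Probability of no events, (1 − p)^10:
  - p = 0.11: 0.89^10 = 0.312
  - p = 0.20: 0.80^10 = 0.107
  - p = 0.30: 0.70^10 = 0.028
  - p = 0.50: 0.50^10 = 0.001
- Probability of at most one event at p = 0.11: 0.312 + 10 × 0.11 × 0.89^9 = 0.697.
- Exact two-sided 95% CI for 0/10: lower limit 0; upper limit 1 − 0.025^(1/10) = 0.308. For 1/10 the exact interval is 0.3% to 44.5%.
- Patients with zero events needed to exclude 11% at one-sided 2.5%: the smallest n with 0.89^n ≤ 0.025 is 32.

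A clean series would exclude rates above about 31%, but would be unremarkable at 11%.

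**5. Would a control arm within 10 patients help?** Assumptions of this review: two-sided 5% test and a halving of the event rate. Splitting 5 v 5 gives power of about 5%, 8% and 12% at control rates of 11%, 30% and 50%. For 80% power the same comparison needs 392, 121 and 58 patients per arm. A control arm at this size would not rescue the objective, so the practical remedy is to match the objective to the data.

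**The case against.** The strongest reply is that the protocol claims little. The objective says evaluate, the study is labelled a pilot, and the analysis is descriptive. A reader might infer that the sponsor plans to declare the OBB better than the alternatives. The documents do not support that: there is no hypothesis, test or success criterion, and item 4's answer options are not shown. Nor is item 4 tied to the efficacy objective. It fits the second primary objective, the clinician's perspective, equally well, and there opinion is the intended target. This stands, and it confines the point to what may be concluded.

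Three further stronger readings also go too far.

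- *The comparator is unnamed and recalled from memory.* Section 5.3 lists topics, and the forms are not in the text. A form might fix the comparator, and the basis for the rating is not stated.
- *Each patient receives oxygen only through the OBB.* The background section on differences from the oral airway says the OBB removes the need for a separate oxygen product, but 5.2 leaves anesthesia management unchanged and no section excludes another source. If one were used, attribution to the OBB would be weaker still.
- *A clean series would show nothing.* At true rates of 30% or 50%, zero events in 10 would be rare (2.8% and 0.1%). It is only the lower part of the range that survives.

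It is also fair to say that efficacy need not mean comparative oxygenation. Ratings of oxygenation, ETCO2 monitoring and teeth protection can be described in one group, and a reworded objective should keep ETCO2 monitoring.

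The objection does not remove the mismatch. Efficacy stands unqualified in 1.0 and 3.0, and nothing in the plan limits the conclusion to descriptive ratings.

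**Conclusion.** The point holds as a mismatch between objective and design. The study can report clinician-rated performance of the OBB in 10 patients. It cannot support a conclusion of efficacy relative to usual oxygen delivery, whatever the ratings or the desaturation count. Confidence in this part is high, because it rests on the stated objective and the absence of any comparator condition.

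The item 4 part holds conditionally: the pooled percentage mixes comparators unless the form names one. Confidence is moderate, because the form cannot be checked.

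The binomial figures illustrate the limit and are not a test that the plan proposes. They depend on treating desaturation and hypoxemia as the same event, and on a background range whose fit to this population is unknown. The title of the reference cited for it concerns ambulatory ASA I-II patients, whereas this study enrols obese ASA I–III patients and lists EUS and ERCP among the procedures. The choice of 10 patients and the lack of a power calculation are not faulted.

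**What to change.** 1. **Objective.** In 1.0 and in primary objective 1 of 3.0, replace the efficacy wording with: *tolerability and clinician-rated adequacy of oxygenation and ETCO2 monitoring with the OBB (descriptive)*. State in 3.0 and 8.3 that no comparative efficacy conclusion will be drawn.
2. **Item 4.** Before the procedure, the anesthesiologist records the oxygen device otherwise planned for that patient (nasal cannula / mask / other). After the procedure, item 4 is rated against that named device. List the answers by comparator and label them as the opinion of study-team raters. Sections 5.2 and 5.3 need updating because they describe questionnaires only after the procedure, and 8.3 because it sets out the reporting. If the form already fixes a comparator, stating it in 5.3 and 8.3 may be enough.

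**Cost.** The study gives up an unqualified efficacy objective and adds one line of pre-procedure data collection. With 10 patients the groups by comparator will be very small, so a listing suits them better than percentages. Patient care does not change.

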## 4.0 Study Population

### 4.1 Inclusion Criteria

Subjects may be included in the study only if they meet ALL of the following criteria:

- Obese patients scheduled to undergo upper endoscopy,
- Willingness and ability to sign an informed consent document,
- ASA class I – III obese adults,
- Subjects will be of diverse racial and ethnic backgrounds.

### 4.2 Exclusion Criteria

Subjects will be excluded from the study for ANY of the following reasons:

- Patients deemed to be at significant airway risk,
- Under 18 years of age since there is no justification to include them,
- Missing or loose incisor or canine teeth
- Temporomandibular joint disease
- Maxillofacial abnormalities (deformities of the jaw, lips, and tongue)
- Pregnant women since there is no justification to include them,
- Emergency surgeries,
- Any other conditions which may interfere with the conduct of the study.

### 4.3 Subject Identification, Recruitment, and Consent

Subjects will be initially identified in the following ways:

- The PI will contact and present the study protocol to endoscopists, and anesthesiologists who are responsible for patients undergoing upper endoscopy, esophageal-gastro duodenoscopy (EGD), endoscopic ultrasound (EUS), or endoscopic retrograde cholangiopancreatography (ERCP) procedures. The day of the procedure the endoscopist or anesthesiologist will hand out the invitation/introductory letter to the patient and explain the study in the preoperative holding area.

If the subject is interested in participating, the endoscopist or anesthesiologist will contact the investigators who will perform the informed consent process. The population will be obese patients at Cedars-Sinai Medical Center. Subjects will be recruited in-person the day of their scheduled endoscopy procedure.

- Recruitment documents will be used: an invitation letter.

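### Section 4.3 gives invitation to the same roles that rate the device, with no consecutive-invitation rule and no count of patients passed over, so selection of lower-risk patients is possible and would go unseen

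*Combined protocol and SAP*

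**What the plan says.** Section 4.3 describes one route into the study. Clinicians responsible for endoscopy patients are told about the protocol, and then "The day of the procedure the endoscopist or anesthesiologist will hand out the invitation/introductory letter to the patient". The next step also runs through them: "If the subject is interested in participating, the endoscopist or anesthesiologist will contact the investigators who will perform the informed consent process".

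Section 4.2 lists eight exclusions. Two depend on judgement: "Patients deemed to be at significant airway risk" and "Any other conditions which may interfere with the conduct of the study". Neither has a criterion, and no section says who applies them.

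The inviting roles are also rating roles. Section 5.2 has the investigators "hand out a short questionnaire to the patient, anesthesiologist, and endoscopist following the procedure". Section 3.0 says of the endoscopist and anesthesiologist: "These professionals will be part of the study team". In section 5.3 the anesthesiologist's questionnaire covers ease of use, "Efficacy of oxygenation of the OBB", oxygenation compared with alternatives, and whether the patient desaturated.

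Sections 8.1 to 8.3 set 10 subjects, claim an exemption from sample size justification as a small pilot, and plan frequencies and percentages. There is no comparator and no success threshold.

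**The concern.** With ten patients and no control group, who is enrolled largely determines how often desaturation is seen. If the clinician who invites has discretion over whom to approach, and the same role then scores oxygenation, a good set of answers may partly reflect easy cases.

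The selection could not be seen or adjusted for afterwards. Section 5.3 limits data to three questionnaires, section 6.1 says no medical record data will be accessed, and section 6.3 adds only diagnosis and treatment date. The procedure table in 5.1 lists demographic information as standard of care, but no section plans to record ASA class, body mass index or airway assessment for analysis.

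Two things are at stake. One is the efficacy part of the first primary objective, as far as it rests on oxygenation and desaturation. The other is feasibility: a reader cannot judge how widely the device can be used in obese endoscopy patients without knowing how many were considered and not enrolled.

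**Working it through.** **Step 1. What controls enrolment.** Sections 4.1 to 4.3.1 and 8.1 to 8.3 contain no consecutive or random invitation, no screening log, and no count of patients eligible, invited or declining. In 4.3, a patient who is not handed a letter has no other described way in. Discretion follows from the absence of a rule; it is not granted in words.

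**Step 2. Which outcomes are exposed.** Section 5.3 lists 3 + 8 + 4 = 15 questionnaire items. Three bear directly on oxygenation: the anesthesiologist's items 3 (efficacy of oxygenation), 4 (the same against alternatives) and 7 (desaturation). Items such as teeth protection, sore throat and interference with the endoscope depend much less on a patient's respiratory risk.

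**Step 3. Plan's own figure.** There is none to reproduce. The 10 subjects come from the pilot exemption in 8.2, without alpha, power or effect size.

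**Step 4. Illustration of size.**

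Inputs from the documents:
- n = 10 (section 8.1).
- A background range of 11% to 50% from section 2.0: "studies showing that hypoxemia occurs in 11–50% of cases".

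Assumptions, not in the documents:
- The desaturation item behaves like the hypoxemia in that range.
- An overall rate p of 30%, within the range, with both ends shown as well.
- A share s = 0.5 of eligible patients is higher risk, at r = 3 to 5 times the risk of the rest.
- Only low-risk patients are invited.
- The device has no effect.

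Formulas:
- Low-risk rate: p_low = p / [(1 − s) + r·s]
- No events without selection: (1 − p)^10
- No events with selection: (1 − p_low)^10

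For p = 0.30:
- No selection: 0.70^10 = 0.028.
- r = 3: p_low = 0.30 / (0.5 + 1.5) = 0.15, and 0.85^10 = 0.197.
- r = 5: p_low = 0.30 / (0.5 + 2.5) = 0.10, and 0.90^10 = 0.349.

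| Overall rate | P(0/10), no selection | P(0/10), selected, r = 3 | P(0/10), selected, r = 5 |
|---|---|---|---|
| 11% | 0.312 | 0.568 (p_low 0.055) | 0.688 (p_low 0.037) |
| 30% | 0.028 | 0.197 (p_low 0.150) | 0.349 (p_low 0.100) |
| 50% | 0.001 | 0.056 (p_low 0.250) | 0.162 (p_low 0.167) |

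**Step 5. What remains without selection.** If no patient desaturates, the exact two-sided 95% upper limit is 1 − 0.025^(1/10) = 0.308. That limit comes from n = 10 alone, whatever the invitation method.

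**The case against.** The strongest reply is that silence is being read as a rule. Section 4.3 says who hands over the letter; it does not say clinicians pick among eligible patients. Section 4.2 does not say they decide the exclusions, and consent is taken by the investigators. That the inviting clinician rates the same case is strongly implied, not stated. All of this stands. A reader might infer that the plan produces hand-picked patients, but the documents show only that it allows them.

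A reader might also infer that ten easy cases would give a favourable result whatever the device does. The documents do not support that. Only three of the 15 items directly concern oxygenation, the patient is also a rater, several other items would expose a poor device even in low-risk patients, and no favourable result is defined.

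A further temptation is to compare ten patients at 11% with ten at 50% and call the gap the effect of selection. Section 2.0 gives a range across studies, which may reflect differing definitions, procedures or sedation as well as patient risk. Neither end represents selected or consecutive enrolment here.

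Two more points are fair. Even perfect consecutive enrolment would leave no comparator and only 10 patients, so device effect and case mix could not be fully separated. And excluding patients at airway risk is not in question; the gap is that such exclusions are not counted.

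The pilot label does not dispose of the matter. Efficacy is part of a primary objective, percentages will be reported, and feasibility needs a denominator even in a pilot.

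**Conclusion.** The point holds as a weakness in the selection method that should be changed. Followed exactly, the plan permits preferential enrolment of lower-risk patients by roles that also rate the device, and it collects nothing that would show whether this happened. The likely bias is mainly in the oxygenation and desaturation percentages. The loss of a denominator for feasibility is certain as the plan is written.

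The size is illustrative only. Under the assumed strata and a 30% overall rate, the chance of 0/10 desaturations rises from 2.8% to about 20–35%. At 11% it is already 31.2% without selection, and at 50% selection brings it only to about 6–16%. These figures depend on complete selection of low-risk patients and on a risk ratio of 3 to 5, neither of which the documents give. They show that selection could matter, not that it will.

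**What to change.** In section 4.3, state that on each study day the clinicians invite every scheduled patient who meets 4.1 and 4.2, in list order, until 10 are enrolled. They keep an identifier-free tally, reported with the results: screened, excluded for airway risk, excluded for other conditions, declined, enrolled. One further line for patients failing any remaining criterion in 4.1 or 4.2 lets the counts add up, so that any shortfall shows eligible patients who were not invited.

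Two places need to be kept consistent:
- The treating clinicians should do the screening, so that the statement in 6.1 that no medical record data will be accessed still holds for the research.
- The line in 4.1 on diverse racial and ethnic backgrounds sits under criteria that every subject must meet. It should be clarified as a description of the population, so that it does not conflict with list order.

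The cost is a tally sheet, a few sentences, less freedom to choose cases and possibly slightly slower enrolment. The sample size, exclusions and procedures do not change. The fix counts the judgement-based exclusions without removing them, does not separate inviter from rater, and supplies no comparator. Those limits, and n = 10, should be acknowledged when the results are reported.
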